#### 11.8 Study Duration and Completion of the Study

The length of the study will be 5.5 years from the date of the first subject entering the study, so subjects will be treated for a maximum of 5.5 years. The end of the study will be the final telephone call (30 days after the last visit) of the last subject or the date the last subject enters the DIUR-015 extension study, which ever is the latest. All subjects must be enrolled by 31 October 2018, with no subjects allowed to enter the study after this date.

Version: 20.0 – 16 Jun 2022 Page **42** of **96** 

#### 11.9 Overdose

In the event of an overdose, the subject should immediately contact the Investigator or Study Nurse for advice. There is no antidote available for Chronocort®.

## 11.10 Subject Diaries

Subjects will be provided with an ad hoc diary in which they will be asked to record any use of sick day medications and to record any AEs that occur between study visits.

#### 11.11 COVID-19 Procedures

Appropriate measures have been put in place to enable the study to continue during the COVID-19 restrictions. Therefore, if necessary, visits can be performed remotely (via telephone or video call) and IMP shipments can be made directly to the subject's home. Safety and endocrine blood sampling can also be performed locally if required (which could include nurses/phlebotomists performing home visits or subjects attending local doctor/general practitioner's office, local endocrinologist's office and local patient centres or clinics) for scheduled 6-monthly visits and dose titrations, to maintain patient safety and consideration of local environmental factors. If local laboratories are used, then normal ranges and certification of the local laboratories will be required. However, prior to implementation of any of these measures Sponsor approval must be obtained.

## 12 Adverse Events and Toxicity Management

## 12.1 Adverse Event Definition

An AE is defined as (21CFR312.32): "Any untoward medical occurrence associated with the use of a drug in humans, whether or not considered drug related." An AE can therefore be any unfavourable and unintended sign (including an abnormal laboratory finding), symptom, or disease temporally associated with the use of a medicinal (investigational) product, whether or not related to the medicinal (investigational) product. This includes any newly occurring event or previous condition that has increased in severity or frequency since the administration of study drug.

#### 12.2 Adverse Event Collection

AEs will be collected for all subjects from the time of consent up to 30 days after the last visit or the early withdrawal visit. Any AEs experienced after this 30-day period should only be reported if the Investigator suspects a causal relationship to Chronocort®. Any ongoing AEs at this point will be followed to resolution or stabilisation if resolution is not expected. Only treatment emergent AEs (i.e. those that started or worsened during Chronocort® treatment in this study) will be included in the main safety analysis: other AEs will be listed.

Details of any AEs, signs, and symptoms will be collected, including details of onset, resolution, frequency, severity, seriousness, relationship to the drug, effect on the study drug, treatments administered, and outcome. All AEs will be followed, whenever possible, until they return to the baseline conditions or become stable with no further changes expected. In the event of any abnormalities considered to be clinically significant by the investigating physician, subjects will be followed up with appropriate medical management until values are considered to be clinically acceptable. Referral or collaborative care will be organised if required.

Version: 20.0 – 16 Jun 2022 Page **43** of **96** 

#### 12.3 Reporting of Adverse Events

Individual AEs should be evaluated by the investigator and recorded in the eCRF. AEs must be reported regardless of whether the investigator thinks the AEs are related to the study treatment.

#### 12.3.1 Diagnoses vs. signs/symptoms

Each AE should be recorded to represent a single diagnosis. Accompanying signs (including abnormal laboratory values if not constituting AEs themselves) or symptoms should NOT be recorded as additional AEs. If a diagnosis is unknown, sign(s) or symptom(s) should be recorded as the AE(s).

#### 12.3.2 Laboratory values

Changes in laboratory values may be considered AEs if they are judged to be clinically significant (i.e., if some action or intervention is required or if the investigator judges the change to be beyond the range of normal physiological fluctuation). If abnormal laboratory values are the result of pathology for which there is an overall diagnosis (e.g., increased creatinine in renal failure), the diagnosis only should be reported as an AE.

#### 12.3.3 Pre-existing conditions

Pre-existing conditions (present before the start of the AE collection period) are considered concurrent medical conditions and should NOT be recorded as AEs. However, if the subject experiences a worsening or complication of such a concurrent condition, the worsening or complication should be recorded as an AE. Investigators should ensure that the AE term recorded captures the change in the condition (e.g., "worsening of....").

#### 12.3.4 Pre-planned surgeries or procedures

Pre-planned procedures (surgeries or therapies) that were scheduled prior to the start of AE event collection are not considered AEs. However, if a pre-planned procedure is performed early (e.g., as an emergency) due to a worsening of the pre-existing condition, the worsening of the condition should be captured as an AE.

#### 12.3.5 Insufficient clinical response (lack of efficacy)

Insufficient clinical response, efficacy, or pharmacological action, should NOT be recorded as an AE. The investigator must make the distinction between exacerbation of pre-existing illness and lack of therapeutic efficacy.

#### 12.3.6 Overdose

Cases of drug overdose without manifested side effects are NOT considered AEs.

#### 12.4 Assessment of Adverse Event Severity

The following guidelines for rating severity of AEs should be used:

#### Mild:

Awareness of signs or symptoms, but easily tolerated; are of minor irritant type; no loss of time from normal activities; symptoms would not require medication or a medical evaluation; signs and symptoms may be transient, disappearing during continued treatment with study medication.

Version: 20.0 – 16 Jun 2022 Page **44** of **96** 

#### Moderate:

Discomfort enough to cause interference with usual activities; the study medication may have been interrupted.

#### Severe:

Incapacitating with inability to do work or do usual activities; signs and symptoms may be of systemic nature or require medical evaluation; the study drug may have been stopped, and treatment for the event may be required.

The term "severe" is often used to describe the intensity of a specific event, as in mild, moderate, or severe myocardial infarction; the event itself, however, may be of relatively minor medical significance, such as severe headache. This is not the same as serious, which is based on subject/event outcome or action criteria usually associated with events that pose a threat to a subject's life or functioning.

#### 12.5 Assessment of Adverse Event Causality/Relatedness

All AEs will be assigned one of the following assessments of causality:

- Not related
- Related to Chronocort®
- Related to sick day medication
- Related to an interaction between Chronocort® and sick day medication
- Related to either Chronocort® or sick day medication
- Related to study medication from previous Chronocort® study

All AEs judged by either the investigator or the sponsor as having a reasonable suspected causal relationship to Chronocort®, or are due to an interaction with Chronocort®, qualify as adverse drug reactions (ADRs).

Appendix 2 provides a comprehensive list of events that are anticipated to occur in the targeted study entry population of subjects with CAH undergoing hydrocortisone replacement therapy. During the course of the trial, if aggregate analyses indicate that the events are occurring more frequently than anticipated, the sponsor will notify Regulatory Authorities expeditiously as appropriate.

#### 12.6 Assessment of Adverse Event Expectedness

An AE is considered "unexpected" if it is not listed in the Reference Safety Information (RSI) in the Investigator's Brochure or is not listed at the specificity or severity that has been observed.

The concept of expectedness does not refer to what may occur in the course of the treated disease such as in the case of disease progression and/or lack of drug effect.

#### 12.7 Serious Adverse Event Definitions

An AE is considered "serious" if, in the view of either the investigator or sponsor, it results in any of the following outcomes (21CFR312.32):

Version: 20.0 – 16 Jun 2022 Page **45** of **96** 

Investigational product: Chronocort®

- Death.
- Is life-threatening. Life-threatening, in the definition of serious, refers to an event in which the subject was at risk of death at the time of the event; it does not refer to an event which hypothetically might have caused death if it were more severe.
- Requires inpatient hospitalisation or prolongation of existing hospitalisation.
- Results in persistent or significant disability/incapacity.
- Is a congenital anomaly/birth defect.
- Important medical events that may not result in death, be life-threatening, or require hospitalisation may be considered serious when, based upon appropriate medical judgment, they may jeopardise the subject and may require medical or surgical intervention to prevent one of the outcomes listed in this definition.

#### 12.8 Suspected Unexpected Serious Adverse Reaction

The definition of Suspected Unexpected Serious Adverse Reaction (SUSAR) includes a suspected causal relationship with administration of the test preparation (thus, a causality assessment of unrelated is not a SUSAR).

#### 12.9 Serious Adverse Event Reporting

As with all AEs, the investigator is responsible for the collection of SAE data. All SAEs should be recorded on the SAE form and the eCRF. Any SAE that occurs between informed consent being signed and 30 days after the last dose of the study treatments (or until the first dose of Chronocort® in the second extension study DIUR-015 for subjects who do not need the 30-day telephone call) must be reported promptly to the sponsor or designee not later than 24 hours after the study site becomes aware of its occurrence, using the SAE form provided. Any SAEs experienced after the 30-day reporting period should only be reported if the Investigator suspects a causal relationship to Chronocort® and treatment with Chronocort® has stopped. All SAEs should be monitored until they are resolved or stabilised.

The initial report shall be promptly followed by detailed, written reports using the SAE report form provided. The initial and follow-up reports shall identify the trial subjects by unique code numbers assigned to the subject. The investigator shall supply the sponsor and the Independent Ethics Committee (IEC)/Institutional Review Board (IRB) with any additional requested information.

The report must be made by telephone, facsimile, or email to the following contacts at the following numbers:

SAEs must be notified immediately (and within 24 hours) by telephone or email to the sponsor's responsible Medical Monitor,

This should be done even if the required information is incomplete or if the investigator is awaiting laboratory or diagnostic reports. This should be followed by a written report within 3 working days.

Version: 20.0 – 16 Jun 2022 Page **46** of **96** 

The SAE form requires the following information (at a minimum):

- Subject ID (case number, gender, date of birth, initials [unless date of birth and initials are not allowed to be collected according to local law])
- Trial no.
- Study therapy (dose, route, form regime, start date, end date)
- Concomitant medication (including dose, route, form, regime, start date where available)
- Nature of SAE (overall diagnosis where available or alternatively signs and symptoms)
- Severity of SAE
- Date and time of occurrence
- Any associated factors (concomitant disease or medication)
- Proposed relationship to study therapy
- Outcome
- Identification of the reporter
- Action in relation to study (withdrawn, suspended, none).

Investigators may be asked for additional information for any report of an SAE. An SAE form indicated as a follow-up report with attached documents (if necessary) should be forwarded to the sponsor/designee as soon as the additional information is available. The sponsor will submit to the Regulatory Authority(ies) all safety updates and periodic reports, as required by applicable regulatory requirement(s).

Some of the AEs likely to occur in subjects with CAH, are of special interest, and whilst they may not be defined as SAEs, they will be reported in the same manner in order to capture the data in real time, together with additional data, if this should be required. However these events will not be reported to the Regulatory Authorities unless they are defined as SAEs. These events will include, but not be limited to, Addisonian crisis and events causing implementation of 'sick day rules'.

Addisonian or adrenal crisis is defined as follows (based on Allolio 2015):

• (A): Major impairment of general health with at least two of the following signs/symptoms:

Hypotension (systolic blood pressure <100 mmHg)

Nausea or vomiting

Severe fatigue

Fever

Somnolence

Hyponatraemia (<132 mmol/L) or hyperkalaemia (as judged by characteristic electrocardiogram [ECG] changes)

Hypoglycaemia

• (B): Parenteral glucocorticoid (hydrocortisone) administration followed by clinical improvement:

Grade 1: outpatient care only

Grade 2: hospital care (general ward)

Grade 3: admission to intensive care unit

Version: 20.0 – 16 Jun 2022 Page **47** of **96** 

Grade 4: death from adrenal crisis (with or without parenteral glucocorticoid administration)

In addition, some events may occur that represent an improvement in the subject's condition e.g. restoration of menses. These events are of special interest and should be recorded as AEs of special interest, clearly stating that the event is an improvement in the condition, and these events will be coded as 'Unexpected Therapeutic Effect'. Whilst these events are not SAEs, they should be reported in the same manner as SAEs in order to capture the data in real time, together with additional data, if this should be required. However these events will not be reported to the regulatory authorities as SAEs.

## 12.10 Serious Adverse Event Expedited Reporting

The sponsor or designee will expedite the reporting to the appropriate Regulatory Authority(ies) of all ADRs that are both serious and unexpected. Such expedited reports should comply with the applicable regulatory requirement(s) (i.e., 21CFR312.32).

#### 12.10.1 Standards for Expedited Reporting

For each SAE/SUSAR, the investigator and sponsor (or designee) will independently assess whether there is a reasonable possibility that the event may have been caused by the study drug ("drug-related"). If the SAE is assessed to be both drug-related and unexpected, the sponsor or designee will report it to the appropriate Regulatory Authorities and notify investigators as required by applicable local regulations. The sponsor or designee will report SAEs to the US FDA as required by 21 CFR 312.32, and EU Competent Authorities as per EU requirements.

SUSARs are required to be reported within 7 calendar days for life threatening events and those resulting in death, or 15 calendar days for all others. These timeframes begin with the first notification of the SUSAR to the sponsor/designee.

All events qualifying as SAEs and SUSARs will be reported by the Pharmacovigilance (PV) Contract Research Organisation (CRO), as necessary, to Regulatory Authorities and IEC/IRB (the latter may be through the local investigator, as required by local regulations). The PV CRO for this study is Bionical-Emas up to the end of March 2022, then Pharmalex from April 2022 onwards.

## 12.10.2 Expedited Reporting Guideline for Other Observations

Other safety issues that might be considered for expedited reporting when they could materially alter the current benefit-risk assessment of the IMP (sufficient to consider changes in the administration or in the overall conduct of the trial) include, for example:

- An increase in the rate of occurrence of an expected serious ADRs, which is judged to be clinically important
- Post-study SUSARs that occur after the subject has completed a clinical trial and are reported by the investigator to the sponsor
- New event relating to the conduct of the trial or the development of the IMP likely to affect the safety of the subjects, such as a SAE which could be associated with the trial procedures and which could modify the conduct of the trial

Version: 20.0 – 16 Jun 2022 Page **48** of **96** 

#### 12.11 Sponsor's Responsibilities

The sponsor is responsible for the ongoing safety evaluation of the IMP. The PV CRO is responsible for ensuring that expedited reports are made to the Regulatory Authority(ies) and all applicable investigators of all ADRs that are both serious and unexpected, of findings that could adversely affect the health of subjects, impact on the conduct of the trial or alter the competent authority's authorisation to continue the trial.

Such expedited reports should comply with the applicable regulatory requirements (e.g., 21CFR312.32). The sponsor should submit to the Regulatory Authority all safety updates and periodic reports, as required by applicable regulatory requirements.

The PV CRO is responsible for arranging structures and written standard operating procedures to ensure that the necessary quality standards are observed in every step of the case documentation, data collection, validation, evaluation, archiving and reporting. The PV CRO will assign a case number to be used in all future correspondence regarding the event and will forward the case to Diurnal Ltd within one working day.

All events qualifying as SUSARs will be reported by the PV CRO, as necessary, to Regulatory Authorities and ethics committees/IRB (the latter may be through the local investigator, as required by local regulations).

#### 12.12 Procedures for Reporting Pregnancy Exposure and Birth Events

Should a female subject become pregnant or be suspected of being pregnant while participating in this study they must be withdrawn from the study immediately (not due to safety reasons but because pregnancy may interfere with the study endpoints) (see Section 11.7). The event must be reported to the sponsor immediately upon receipt of information by the study staff using the pregnancy form. While the pregnancy itself is not considered to be an AE or SAE, any pregnancy complications should be recorded as AEs or SAEs (if applicable). Any pregnancy will be followed through delivery for the observation of any SAEs. Fatalities and spontaneous abortions must be reported as SAEs.

#### 12.13 Data Safety Management Board

An independent DSMB will meet on a regular basis during the study in order to review safety data. The DSMB will operate in accordance with a charter.

#### 13 Statistical Considerations

A detailed and comprehensive statistical analysis plan (SAP) will be prepared and signed-off before the first subject has given informed consent for this extension study. Minor changes to the statistical methods set out in this protocol need not be recorded as a protocol amendment but must be documented in the SAP and in the study report.

Interim data analyses are expected to be required for regulatory review as part of any marketing authorisation applications. No changes to the overall study conduct and no changes to the planned formal statistical analyses are anticipated as a result.

Version: 20.0 – 16 Jun 2022 Page **49** of **96** 

The statistical analysis will be undertaken by The statistical analysis and report will conform to the relevant ICH requirements, including but not limited to those set out in ICH documents E3 and E9. SAS version 9.2 or later will be used for the analysis.

#### 13.1 Conventions and Methods

#### 13.1.1 Summary Tables, Listings and Figures

The standard summary statistics for continuous baseline and outcome variables are: N, mean, standard deviation (SD), median, quartiles, minimum and maximum. The standard summary statistics for categorical baseline and outcome variables are: count and proportion (expressed as percentage). Geometric mean and coefficient of variation will also be presented for variables which will subsequently be log-transformed during the analysis.

Summary tables and figures will be supported by full subject listings.

Data will be summarised according to time since first dose of Chronocort® treatment (which may have been in the feeder study for study DIUR-005). Time slotting will be described in the SAP.

Safety and efficacy parameters will be explored based on previous treatment in the feeder study and by previous standard therapy. Exploratory analyses will also be undertaken to assess the relationship between disease control and the proportion of daily dose given at night. Further details will be provided in the SAP.

For subjects who re-enter the study post-pregnancy, data collected during the post-pregnancy phase will be listed only. Only data up to the time of first study withdrawal will be included in summary tables and figures. Individual subject profiles will be created to support discussion of data from this small subset of subjects in the clinical study report.

Disruptions due to the COVID-19 pandemic will be summarised by feeder study and previous treatment. The summary will include an overview of study visit or study medication disruptions due to the COVID-19 pandemic, as well as including whether the scheduled visit was delayed or scheduled assessments were not done. Detailed listings of study visit disruptions and study medication disruptions will be produced.

#### 13.1.2 Hypothesis Testing and Confidence Intervals

Since all subjects participating in this trial will be receiving Chronocort®, there will be no formal treatment comparisons. Summaries over time will be produced for safety and efficacy parameters.

#### 13.1.3 Missing Outcome Data

Blood samples for analysis of 17-OHP and A4 values are to be taken at 09:00 and 13:00, with a window of +/- 1 hour allowed. Missing 17-OHP and A4 values (including those considered missing due to being taken outside the permitted time window) will not be imputed. In calculating the mean of the 09:00 and 13:00 SDS, if one value is missing, then only the non-missing value will be used. If both values are missing, the mean value will be missing.

#### 13.2 Analysis Sets

The full analysis set comprises all subjects who entered the study and who subsequently Version: 20.0 - 16 Jun 2022 Page **50** of **96** 

received at least one dose of Chronocort®. Subjects in the full analysis set will be analysed according to the actual treatment received.

The interim analysis set is a subset of the full analysis set. In addition to entering the study and receiving at least one dose of Chronocort®, subjects must also have completed the Week 24 (Visit 4) assessment or discontinued early from treatment and withdrawn from the study (Interim Analysis 1). For subsequent interim analyses, a data cut-off date will be defined for each interim analysis set. At the time of interim analyses, all primary, secondary and exploratory endpoints will be summarised using the interim analysis set. Subjects in the interim analysis set will be analysed according to the actual treatment received.

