6.2. Interim analysis set

The interim analysis set is a subset of the full analysis set. In addition to entering the study and receiving at least one dose of Chronocort®, subjects must have also completed the Week 24 (Visit 4) assessment or discontinued early from treatment and withdrawn from the study at the specified data cut-off requested for the interim analysis.

At the time of interim analyses all primary, secondary and exploratory endpoints will be summarised using the interim analysis set. Subjects in the interim analysis set will be analysed according to the actual treatment received. The interim analysis set will be used for all interim analyses carried out in this study.

7. Treatment comparisons

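### For cut-offs before about May 2019, the interim analysis set counts a subject with under 24 weeks in study only if already withdrawn, so interim safety tables depend on outcome

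*Protocol*

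**What the plan says.** Protocol 13.2 defines the interim set as a subset of the full analysis set. Besides entering and taking at least one dose, "subjects must also have completed the Week 24 (Visit 4) assessment or discontinued early from treatment and withdrawn from the study"; the label Interim Analysis 1 follows in parentheses. For later interims the protocol says only this: "For subsequent interim analyses, a data cut-off date will be defined for each interim analysis set". It does not say whether the Week 24 condition still applies.

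SAP 6.2 repeats the condition without that label. It judges whether a subject has "discontinued early from treatment and withdrawn from the study at the specified data cut-off requested for the interim analysis", and adds: "The interim analysis set will be used for all interim analyses carried out in this study".

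Protocol 13.2 states "At the time of interim analyses, all primary, secondary and exploratory endpoints will be summarised using the interim analysis set", and SAP 6.2 says the same in substance. The primary endpoint is safety (Protocol 13.3.1). In SAP Appendix A, the adverse event tables, adverse events leading to discontinuation, adrenal crises per 100 patient years and the adverse event listing all use the interim set at an interim. Subject disposition (Table 14.1.1) is on all subjects.

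Protocol 13 gives the purpose: "Interim data analyses are expected to be required for regulatory review as part of any marketing authorisation applications".

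**The concern.** Entry was staggered from August 2016 to 31 October 2018. At a cut-off in or soon after that period, some dosed subjects have not reached Week 24. The rule leaves out those still on treatment and keeps those who have left, so membership depends on an outcome.

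Suppose two subjects each have an adrenal crisis at Week 10. If one then withdraws and the other stays on Chronocort, only the first appears in the interim tables and listing. None of the event-based primary endpoints needs a Week 24 visit. The protocol synopsis also relates adverse event rates to the number of subjects treated, which this set is not.

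The lost time is early time on study. For subjects from DIUR-003, from the DIUR-005 standard-therapy arm and those with a gap, it covers the switch from another glucocorticoid and the first titrations. These are the tables meant for regulators.

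**Working it through.** **Inputs from the documents.** Maximum N = 16 + 122 = 138 (Protocol 13.7). First entry is August 2016 (synopsis) and last permitted enrolment 31 October 2018 (11.8). The Week 24 window is ±2 weeks (11.1). Neither document gives an interim cut-off, interim size or discontinuation rate, so there is no plan figure to reproduce.

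**Who is counted.** For a subject dosed less than 24 weeks before the cut-off:
- discontinued and withdrawn: in the set;
- still on Chronocort: out of the set.

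For a subject dosed longer ago, still on Chronocort, with Week 24 missed: out of the set if the condition is read literally.

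**Direction.** Let N be subjects dosed, D those discontinued, and R_on those ongoing before Week 24. The share on the interim set is D/(N − R_on), which is at least D/N. Let M be the subjects with 24 weeks elapsed, p the true 24-week risk, and R_d the recent entrants already gone. The interim-set share is (Mp + R_d)/(M + R_d), which is at least p. The upward direction for a discontinuation percentage does not depend on the model below.

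**When it can occur.** Taking 31 October 2018 as the last first-dose date, adding 168 days gives 17 April 2019, and 14 more days for the window gives 1 May 2019. After that no recent entrants remain.

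**Size (assumed model).** Assumptions: 138 subjects entering evenly from 1 August 2016 to 31 October 2018 (821 days); a constant discontinuation hazard; everyone ongoing past 24 weeks has completed the Week 24 visit; only discontinuation before Week 24 is counted.
- Recent entrants during the entry period: R = 138 × 168/821 = 28.2.
- Already gone: R_d = R × [1 − p/(−ln(1 − p))]. For p = 10%, this is 28.2 × (1 − 0.100/0.1054) = 1.4, so R_on = 26.8.
- Example cut-off 28 June 2018 (the SAP version 2.0 date, used only for illustration): N = 138 × 696/821 = 117.0 and M = 117.0 − 28.2 = 88.8.
- Interim-set share: (8.9 + 1.4)/(88.8 + 1.4) = 11.4%.
- Crude share on all dosed: (8.9 + 1.4)/117.0 = 8.8%. This is low because follow-up is incomplete.

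| Assumed cut-off | Dosed | Ongoing and omitted | True 5% shows as | True 10% | True 20% |
|---|---|---|---|---|---|
| 31 Dec 2017 | 87 | 25–28 (29–32%) | 6.1% | 12.2% | 23.8% |
| 28 Jun 2018 | 117 | 25–28 (22–24%) | 5.8% | 11.4% | 22.6% |
| 31 Oct 2018 | 138 | 25–28 (18–20%) | 5.6% | 11.2% | 22.1% |
| 25 Jan 2019 | 138 | 12–13 (8–10%) | 5.4% | 10.8% | 21.4% |
| 21 Jun 2019 | 138 | 0 | 5.0% | 10.0% | 20.0% |

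For cut-offs within the entry period, omitted person-time is about 27 subjects × 12 weeks on average ÷ 52, or roughly 6 person-years. In the table of adverse events leading to discontinuation, p is the risk of that type of discontinuation. Withdrawals for other reasons enlarge the denominator and dilute the inflation somewhat.

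**The case against.** Several points on the other side stand.

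- **Disposition.** A reader might infer that the interim withdrawal rate is overstated. The documents do not support that: the withdrawal summary (Table 14.1.1) is on all subjects. The exposed percentages are those on the interim set, chiefly adverse events and serious adverse events leading to discontinuation.
- **Scope.** A reader might also infer that both documents apply the rule to every interim. Only the SAP does; the protocol ties it to Interim Analysis 1 and is silent on later ones.
- **Missing events.** These do not imply understated adverse event percentages. The omitted subjects leave the denominator too, and their person-time leaves the crisis rate per 100 subject-years, so crude percentages may rise. The discontinuation bias works against the drug.
- **Timing.** The current texts date from June and July 2022, after the staggered-entry window had closed. Rewording them now cannot change a future interim through that route.
- **Other safeguards.** Adverse event listings go to the safety board on an ongoing basis (Protocol 14.7), serious events and adrenal crises are reported to the sponsor promptly (12.9), and the final analysis uses all dosed subjects (SAP 6.1). SAP Appendix A plans an analysis-set table (14.1.3) and a listing of excluded subjects (16.2.3).

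These limit the harm but do not remove it. The exclusion listing shows who is missing, while the adverse event listing, itself on the interim set, does not show what happened to them. The safety board's listings and the final report do not correct interim tables already prepared for a marketing application.

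**Conclusion.** The concern holds for Interim Analysis 1 under the protocol and for every interim under SAP 6.2. Interim primary safety tables and listings leave out events and person-time in subjects still on treatment before Week 24. Discontinuation-type percentages on that set are biased upward. The disposition table and the final analysis are not affected.

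The staggered-entry effect is confined to cut-offs before about 17 April to 1 May 2019. The amendment history shows that interim analyses had been run by September 2019 but gives no cut-offs, so whether any fell inside the window cannot be settled from the documents. After that date, what remains is the SAP's exclusion of an ongoing subject who missed Week 24; the number of such subjects is not stated.

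The size rests wholly on assumptions. Across true rates of 5 to 20%, the overstatement is about 0.4 to 3.8 percentage points for cut-offs that leave anyone out. Even entry is a simplification, because DIUR-005 subjects entered as they completed that study; clustered entry would change the numbers omitted. The study is descriptive, so no test is invalidated. The point should be corrected because the affected endpoint is the primary one and the tables were meant for regulators.

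**What to change.** In Protocol 13.2 and SAP 6.2:

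1. Summarise interim safety endpoints on all subjects dosed by the cut-off. Beside the crude n (%), show rates per 100 subject-years or time-to-event summaries. The adjustment is needed: in the June 2018 example, the crude all-dosed share is 8.8% against a true 10%, an error nearly as large as the 11.4% on the interim set but in the other direction.
2. Define any Week 24 efficacy set by first-dose date, at least 26 weeks (24 plus the 2-week window) before the cut-off, whatever the subject's status or attendance.
3. Use one definition for later interims in both documents.
4. Re-run the safety tables of any interim with a cut-off before about May 2019, or add a note stating how many dosed, ongoing subjects were left out and what events they had.

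The cost is a wording change and reprogramming on data already held. The downside is that crude percentages will include subjects with short follow-up, so the exposure-adjusted figures must appear with them.
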